#### **4.1.3 Blinding**

Botanix, the clinical research organization (CRO), the investigator, study site personnel and subjects will be blinded to the treatment assignment. The randomization schedule will be kept strictly confidential and accessible only to authorized persons. Only when the study has been completed, the protocol violations determined, evaluability confirmed, and the study database locked will the randomization schedule be released for analysis.

During the study, the randomization code will not be broken except in the case of a safety concern, either for an individual subject or for the entire study. If a subject has an adverse event (AE) that may necessitate unblinding of the randomization code, the site will contact the CRO and Botanix to discuss if there are options other than unblinding. If the site and Botanix agree that unblinding is in the best interests of the subject, the IWRS system will be used to obtain treatment assignment information. The Medical Monitor must be notified whenever study medication is unblinded, preferably prior to unblinding a subject.

### **5. EFFICACY AND SAFETY ENDPOINTS**

#### **5.1 Efficacy Endpoints**

##### **5.1.1 Primary Efficacy Endpoints**

The primary efficacy endpoint for the study is:

- The proportion of subjects with Investigator Global Assessment (IGA) success defined as an IGA score of “Clear” (0) or “Almost Clear” (1) with at least a 2-grade improvement from Baseline at Day 85

### **5.1.2 Secondary Efficacy Endpoints**

The secondary efficacy endpoints for the study are:

- The change from Baseline in the total Signs of AD score at Day 85,
- The proportion of subjects with an IGA of Clear or Almost Clear at Day 85,
- The proportion of subjects with at least a 2-grade improvement in IGA from Baseline at Day 85,
- The change from Baseline in the percent of total body surface area (BSA) affected by AD at Day 85,
- The time to achieve IGA success, and
- The change from Baseline to Day 85 in the Itch-Numerical Rating Scale (I-NRS).

### **5.1.3 Exploratory Efficacy Endpoints**

The exploratory endpoints for the study are:

- The change from Baseline in the total Signs of AD score at Day 15, Day 29, and Day 57,
- The change from Baseline in the percent of total BSA affected by AD at Day 15, Day 29, and Day 57
- The proportion of subjects with IGA success defined as an IGA score of “Clear: (0) or “Almost Clear” (1) with at least a 2-grade improvement from Baseline at Day 15, Day 29, and Day 57,
- The change from Baseline to Day 29 and Day 57, and Day 85 in the Signs of AD score for the target lesion (at selected sites only).

## **5.2 Safety Endpoints**

Safety will be assessed through adverse events (AEs), complete blood count (CBC), chemistry, and urinalysis laboratory tests, and reports of burning/stinging obtained during visits on Day 1, Day 15, Day 29, Day 57, and Day 85 (within AEs).

## **6. STATISTICAL AND ANALYTICAL PLANS**

### **6.1 General Methodology**

All statistical processing will be performed using SAS® 9.4 or higher. No interim analyses are planned. This Phase 2 study is designed to identify the response of BTX 1204 4.0% BID compared to Vehicle BID. Statistical tests will be exploratory. No adjustments for Type I error will occur.

Descriptive statistics will be used to provide an overview of the efficacy and safety results. For categorical parameters, the number and percentage of subjects in each category will be presented. For continuous parameters, descriptive statistics will include n (number of subjects), mean, standard deviation (SD), median, minimum and maximum.

The primary method of handling missing efficacy data in the Intent-to-Treat (ITT) and modified Intent-to-Treat (mITT) analysis sets will be based on last observation carried forward (LOCF). Repeated measures analyses will be used on the observed data as a sensitivity analysis on the primary endpoint.

The efficacy analysis performed on the ITT population is considered the primary analysis. The efficacy analyses performed on the mITT and per-protocol (PP) populations are considered supportive analyses.

The number of subjects in each analysis set will be summarized. Reasons for study withdrawal during the study will be summarized using frequencies and percentages by treatment group.

Reported AEs, medical history terms and prior and concomitant procedures and therapies will be classified on the basis of Medical Dictionary for Regulatory Activities (MedDRA) terminology. Prior and concomitant medications will be classified on the basis of World Health Organization Drug Dictionary (WHO-DDE) terminology.

#### **6.1.1 Statistical Analysis**

All analyses will be performed by QST using SAS® Version 9.4 or later. All summary tables and data listings will be prepared utilizing SAS® software.

The standard operating procedures of QST will be followed in the creation and quality control of all data displays and analyses.

#### **6.1.2 Baseline Definition**

Baseline is defined as the last non-missing assessment prior to first application of study drug.

### 6.1.3 Visit Windowing

Data will be summarized based on nominal visit indications with the exception of data captured at early termination and unscheduled visits. Data from early termination and unscheduled visits will be summarized based on mapped visit values. The analysis windows for early termination and unscheduled visits are presented in the following table.

**Analysis Windows for Efficacy and Safety Assessments**

Scheduled Visit	Target Study Day	Window (Days)
Day 15	15	9 to 21
Day 29	29	22 to 42
Day 57	57	43 to 70
Day 85	85	71 to 98

Data collected at early termination and unscheduled visits prior to study day 9 will not be analyzed, with the exception of those identified as Baseline values. Efficacy and safety data collected at early termination and unscheduled visits after study day 98 will not be included in analyses.

The definition for the study day included in each study window is defined as below:

Study Day prior to Day 1 = Visit Date – Day 1 Date

Study Day on or after Day 1 = Visit Date – Day 1 Date + 1

If an assessment's mapped visit is a visit at which the subject has data from a scheduled visit present, or if no analyses are planned for the assessment at the mapped visit, the data collected at the early termination or unscheduled visit will not be included in analyses.

In the event of multiple values from unscheduled or early termination assessments within an analysis window, the value closest to the scheduled visit target study day will be used for analyses. If two values tie as closest to the time point (for example, one value is before and the other value is after the time point), then the later value will be selected.

Data collected at all visits will be included in the data listings with visit presented as reported by the site.

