#### **6.1.5 Handling of Dropouts or Missing Data**

All efforts will be made to minimize the occurrence of missing data. It is not expected that dropout rates will differ between groups. Therefore, the primary method of handling missing efficacy data in the ITT and mITT analysis set will be based on LOCF. Summary of efficacy variables for the PP subjects will be based on available data. No imputation will be done for non-efficacy related variables.

If a partial date is reported where the day is missing, then the day will be imputed as the first day of the month unless the month is the same month as the first application of study drug then the day will be that of first application with the month and year remaining the same. If a partial date is reported where the month is missing, then the month will be imputed to January unless the year is the same year as the first application of study drug then the month will be that of first application with the year remaining the same. If a partial date where both the day and month is missing, follow details as stated previously.

Missing AE start dates will be imputed using partial date imputation rules as previously described in this Section.

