## **6.8 Analysis of Efficacy**

The efficacy analyses will be performed using the ITT (primary), mITT (supportive), and PP (supportive) populations. The IGA, total BSA affected by AD, Signs of AD total score, and I-NRS analyses will employ the methods for handling missing data as described in Section 6.1.5. IGA, total BSA affected by AD, Signs of AD score, and I-NRS data will also be shown in by-subject listings.

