#### **6.10.1 Repeated Measures**

The first sensitivity analysis for the primary endpoint, IGA success, will be analyzed using a repeated measures logistic regression (generalized estimating equations), with dichotomized IGA success as the dependent variable and treatment group, visit, and treatment group by visit interaction as independent factors. In this analysis, data from all post-Baseline visits will be included with no imputation for missing data.

```
proc genmod data = datain;
  class SUBJECT TRT VISIT;
  model IGA SUCCESS = TRT VISIT TRT * VISIT / dist=bin;
  repeated subject = SUBJECT/type = cs;
  lsmeans TRT*VISIT / diff;
  estimate 'pval' TRT 1 -1 TRT*VISIT 0 0 1 0 0 -1;
run;
```

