#### **6.10.2 Tipping Point**

A tipping point analysis of the primary endpoint, proportion of subjects with IGA success defined as an IGA score of Clear (0) or Almost Clear (1) with at least a 2-grade improvement from Baseline at Day 85, will be performed as a sensitivity analysis for the handling of missing data. Specifically, a range of response rates for both groups will be explored to determine the tipping point(s) at which the combinations result in no longer reaching statistical significance.

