## 11. INDEX OF PLANNED FIGURES

Figure 14.2.1.5: Sensitivity Tipping-Point Analyses of the Primary Efficacy Endpoint: Dichotomized IGA Success at Day 85 (Intent-to-Treat Population) ..	103
Figure 14.2.2.4.4: Secondary Endpoint: Kaplan Meier Curves for Time to IGA Success (ITT Population) .....	104
Figure 14.2.2.4.5: Secondary Endpoint: Kaplan Meier Curves for Time to IGA Success (mITT Population) .....	105
Figure 14.2.2.4.6: Secondary Endpoint: Kaplan Meier Curves for Time to IGA Success (PP Population) .....	105

[figure not shown]
Figure 14.2.1.5: Sensitivity Tipping-Point Analyses of the Primary Efficacy Endpoint: Dichotomized IGA Success at Day 85 (Intent-to-Treat Population)

Note: The horizontal and vertical axes indicate the potential number of successes among subjects with missing data in each treatment group. Each plotted point indicates the number of imputed successes in each treatment group that results in a p-value greater than 0.05. The red lines represent the number of imputed successes from the primary analysis using last observation carried forward (LOCF) to impute missing values.

SOURCE: USERNAME/SPONSOR/PROJECT/JOBNAME (DATE,TIME)

Figure 14.2.2.4.4: Secondary Endpoint: Kaplan Meier Curves for Time to IGA Success (ITT Population)

Note: Circles represent censored observations.  
SOURCE: USERNAME/SPONSOR/PROJECT/JOBNAME (DATE,TIME)

Repeat Table 14.2.2.4.4 for the following:

Figure 14.2.2.4.5: Secondary Endpoint: Kaplan Meier Curves for Time to IGA Success (mITT Population)

Figure 14.2.2.4.6: Secondary Endpoint: Kaplan Meier Curves for Time to IGA Success (PP Population)

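### Read literally, the visit-window rule in SAP 6.1.3 discards some early-termination scores, so LOCF can carry a Day 85 value older than the last score observed

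*SAP*

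**What the plan says.** SAP 6.1.3 keeps scheduled visits under their nominal label and treats other visits differently: "Data from early termination and unscheduled visits will be summarized based on mapped visit values". The windows are Days 9 to 21 (Day 15), 22 to 42 (Day 29), 43 to 70 (Day 57) and 71 to 98 (Day 85). Two exclusions follow:

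- If the mapped visit already has scheduled data for that subject, "the data collected at the early termination or unscheduled visit will not be included in analyses".
- For very early values, apart from those that serve as Baseline, "Data collected at early termination and unscheduled visits prior to study day 9 will not be analyzed".

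The closest-to-target rule in the same section chooses only among several ET or unscheduled values. It does not restore an ET value that has lost to a scheduled one. All visits still go to the listings.

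SAP 6.1.5 states that "the primary method of handling missing efficacy data in the ITT and mITT analysis set will be based on LOCF". It does not say which observations may be carried. SAP 6.8 refers back to it: "The IGA, total BSA affected by AD, Signs of AD total score, and I-NRS analyses will employ the methods for handling missing data". Neither SAP section 8 nor the protocol (Summary and 9.3.8) adds a rule on what LOCF may use.

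ET scores should exist. The protocol Summary, Section 4.3 and Table 4 footnote b all call for Day 85 assessments at early exit.

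**The concern.** LOCF is meant to carry the last observation. Under the literal text, a dropout who leaves after a completed visit in the same window has that earlier visit carried instead, and the later exit score is set aside. Two subjects with identical scores can then be classified differently because one left a day later.

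The setting is plausible. The disposition shell (Table 14.0.1) lists worsening condition as a reason for discontinuation. An ET score may record the very deterioration that led to exit, and the rule can replace it with an earlier, better score. The reverse can also happen.

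The planned checks do not repair this:

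- **Repeated measures (6.10.1):** "The first sensitivity analysis for the primary endpoint, IGA success" uses no imputation, but under 6.1.3 it also omits the discarded ET values.
- **Tipping point (6.10.2):** "A tipping point analysis of the primary endpoint" spans the possible success counts among subjects with missing data. The primary estimate and p-value still rest on the older scores, and so do the reference lines in Figure 14.2.1.5: "The red lines represent the number of imputed successes from the primary analysis using last observation carried forward (LOCF) to impute missing values".
- **Secondary endpoints:** Signs of AD total score, BSA and I-NRS use the same LOCF, and neither sensitivity analysis is planned for them.

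**Working it through.** The documents give no dropout rate, ET timing or power calculation, so there is no plan figure to reproduce. The check applies the SAP 6.1.3 rules to each possible exit day.

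**Inputs**

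- Analysis windows 9–21, 22–42, 43–70 and 71–98 (SAP 6.1.3).
- Scheduled visits on Days 15 ±3, 29 ±3 and 57 ±5 (protocol Table 4).
- Baseline IGA 3 (protocol inclusion criterion 5). Success is IGA 0 or 1 with an improvement of at least 2 grades.

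**Effect on one subject**

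| Last scheduled score | ET score and day | ET maps to | Day 85 value under the rule | Status under the rule | Status from last observed score |
|---|---|---|---|---|---|
| IGA 1, Day 57 | IGA 3, Day 70 | Day 57 (occupied) | 1 | success | failure |
| IGA 1, Day 57 | IGA 3, Day 71 | Day 85 (empty) | 3 | failure | failure |
| IGA 2, Day 29 | IGA 1, Day 38 | Day 29 (occupied) | 2 | failure | success |

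**Exit days that matter**

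ET values before Day 9 are not analysed, and those on Days 71–98 map to Day 85 and need no carrying. That leaves Days 9–70, which is 62 days, less the three visit days: 62 − 3 = 59.

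**Days on which the ET score is dropped, visits on target**

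- Day 15 window: Days 16–21, 21 − 15 = 6
- Day 29 window: Days 30–42, 42 − 29 = 13
- Day 57 window: Days 58–70, 70 − 57 = 13
- Total 6 + 13 + 13 = 32, and 32/59 = 54.2%

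The ET score is used on Days 9–14, 22–28 and 43–56: 6 + 7 + 14 = 27, and 27 + 32 = 59.

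**Range over the permitted visit days**

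- Latest (18, 32, 62): 3 + 10 + 8 = 21, and 21/59 = 35.6%
- Earliest (12, 26, 52): 9 + 16 + 18 = 43, and 43/59 = 72.9%

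All 539 combinations of permitted visit days (7 × 7 × 11) lie between these limits.

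**Age of the carried score relative to the discarded one**

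On target the lags run 1–6, 1–13 and 1–13 days. Their sum is 21 + 91 + 91 = 203, and the mean is 203/32 = 6.3 days, with a maximum of 13. If Day 57 was held on Day 52, the maximum is 70 − 52 = 18 days.

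**Other denominators, same 32 days**

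- Days 16–84 without visit days: 32/67 = 47.8%
- Days 9–84 without visit days: 32/73 = 43.8%
- Days 2–84 without visit days: 32/80 = 40.0%

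**Weight of one subject**

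With 100 per arm, one reclassified subject moves that arm's success rate by about 1/100, or 1 percentage point.

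**The case against.** The strongest reply is that 6.1.3 opens by saying how data will be summarized. On that reading the windows only fill by-visit slots, and LOCF may still use any observation, so the defect is only an unstated LOCF source rule. A programmer could read it that way. But the exclusion itself refers to analyses without limit, and the section separately reserves such values for the listings. The authors could be explicit elsewhere: SAP 6.8.2.5 ties censoring to the last recorded assessment. If two programmers can build different primary datasets, the text needs settling in any case.

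Other points, and what remains of them:

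- **The rule is pre-specified, the same in both arms, and every window has an edge.** True. It guards against data-driven choice, but it does not make the carried value the last one.
- **An ET score may follow other AD treatment (protocol 6.6).** True, but a scheduled score may also follow such treatment and is already eligible to be carried.
- **The 54% depends on the denominator.** It does, and the alternatives are shown above. The 59-day base is reasonable because it holds the exit days on which an analysable ET score would have to be carried to reach Day 85.
- **The PP analyses repeat every endpoint without LOCF.** They do, but PP is largely a completer set and so says little about dropouts.
- **The tests are exploratory, and I-NRS is only described.** This lowers the stakes.
- **The trigger is scheduled data at the mapped nominal visit, not a visit date inside the window.** Correct. A Day 29 visit held late on Day 45 would not block an ET score on Day 50. The counts above assume visits within the protocol windows, where the two descriptions agree.

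**Conclusion.** The concern holds. Followed as written, SAP 6.1.3 and 6.1.5 can give a Day 85 LOCF value older than the last observed score, and the subject's primary classification can change with the exit day. Between 21 and 43 of the 59 relevant exit days are affected, 32 with visits on target.

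This rests on the literal reading of the exclusion and on scheduled visits held within the protocol windows. The figures are shares of calendar days, not of subjects. The number of subjects affected and the net direction cannot be derived, because the documents give no dropout rate, exit timing or ET completion. The comparison is with the last observed score; a dropout's true Day 85 status is unknown. For an exploratory Phase 2a trial this should be fixed, but it does not invalidate the design.

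There is a related gap. A subject whose only post-Baseline efficacy score is an ET or unscheduled value before Day 9 meets the ITT definition in SAP 6.4.2, yet that score is not analysed and the SAP does not say how the subject is handled.

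**What to change.** Add to SAP 6.1.3 and 6.1.5:

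> *The rule that gives precedence to scheduled visits governs by-visit summaries only. LOCF carries the chronologically last non-missing post-Baseline assessment on or after study Day 9 and before the visit being imputed, including ET and unscheduled values whose mapped visit holds scheduled data.*

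Keep the pre-Day-9 exclusion, and add one sentence aligning it with SAP 6.4.2 on how a subject with only an earlier value is handled.

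The cost is three sentences before unblinding. No new data are needed, because every visit is already collected and listed. Some dropouts' Day 85 values may change, in either direction.

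A separate data-collection point: protocol 6.3.8 restricts the attempt at ET assessments to exits for reasons other than an AE, while the Summary, Section 4.3 and Table 4 footnote b make no such restriction. These passages must be reconciled.

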#### **6.1.4 Adjustments for Covariates**

Baseline total BSA affected by AD will be a covariate for the secondary efficacy endpoint, change from Baseline in total BSA affected by AD. Baseline Signs of AD total score will be a covariate for the secondary and exploratory efficacy endpoints change from Baseline in total Signs of AD. No other covariates are planned to be used in the analyses for this study.

#### **6.1.5 Handling of Dropouts or Missing Data**

All efforts will be made to minimize the occurrence of missing data. It is not expected that dropout rates will differ between groups. Therefore, the primary method of handling missing efficacy data in the ITT and mITT analysis set will be based on LOCF. Summary of efficacy variables for the PP subjects will be based on available data. No imputation will be done for non-efficacy related variables.

If a partial date is reported where the day is missing, then the day will be imputed as the first day of the month unless the month is the same month as the first application of study drug then the day will be that of first application with the month and year remaining the same. If a partial date is reported where the month is missing, then the month will be imputed to January unless the year is the same year as the first application of study drug then the month will be that of first application with the year remaining the same. If a partial date where both the day and month is missing, follow details as stated previously.

Missing AE start dates will be imputed using partial date imputation rules as previously described in this Section.

#### **6.1.6 Interim Analyses and Data Monitoring**

No interim analysis or data monitoring is planned for this study. Blinded subject data will be reviewed as it is generated to monitor for any safety signals and to ensure that the study is being appropriately executed.

#### **6.1.7 Multicenter Studies**

This study will be conducted at multiple investigational sites in the United States (US), Australia (AUS) and New Zealand (NZ) with the intention of pooling the results for analysis.

### **6.1.8 Multiple Comparisons/Multiplicity**

This Phase 2a study is designed to identify the response to BTX 1204 relative to vehicle. Statistical tests applied to the outcomes will be exploratory. No adjustments for Type 1 error will occur.

### **6.1.9 Use of an Efficacy Subset of Subjects**

One subset of interest is the mITT population. This subset is defined in order to better assess the effects of treatment on target areas; see Section 6.4.3 for definition.

Subjects randomized to study drug who complete the Day 85 visit without noteworthy study protocol violations, including compliance with study drug application, and completion of efficacy evaluations on Day 85 will form the PP population. Any noteworthy protocol violations will be defined at the time of evaluability evaluation, the time between the database soft lock and hard lock before unblinding.

Both mITT and PP analyses will allow for a further exploration of overall efficacy of BTX 1204.

### **6.1.10 Active-Control Studies Intended to Show Equivalence**

Not applicable to this study.

### **6.1.11 Examination of Subgroups**

Subset analyses will be conducted for the mITT and PP analysis sets on the primary efficacy endpoint. These analyses will be summarized using descriptive statistics. The specific subsets within the mITT and PP analysis sets that will be evaluated include:

- Geographical region (US vs AUS/NZ);
- Gender (Male vs. Female);
- Ethnicity (Hispanic or Latino vs Non-Hispanic or Latino);
- Race (White vs Non-White)
- Age (12 to < 18 Years vs. 18 to < 30 Years vs.  $\geq$ 30 Years)

